## 6.5. Withdrawal Criteria

If a participant wishes to withdraw from the study then no further data (aside from safety data) will be collected with regards to that individual. The PD catheter will remain in situ until such time as it is decided by the clinical team that it should be removed for clinical reasons.

Participants will be withdrawn from the study if they have the PD catheter removed for any reason. The study may be stopped early if there is a concern about safety/tolerability of the novel PD catheter.

#### 6.6. Storage and Analysis of Samples

Stored samples will consist of:

#### **Positive Microbiology Isolates**

After incubation of culture plates from PD fluid (undertaken as standard of care in the microbiology lab at UHDB), the plates should be secured by means of adhesive tape to ensure that the lids remain in place, and placed in a secure transit container (available from either UoN or Derby clinical laboratory). They should then be transmitted promptly (within 24hr) to the laboratory at UoN. Films prepared for microscopy examination of the PD fluid should be placed in a slide carrier and this placed in a secure container for transit with the plates, and accompanied by the initial request form and any notes and observations from the Derby clinical laboratory.

On arrival at the research laboratory at UoN, the plates will be allotted a serial number and this entered in a register. They will then be examined by a microbiology-trained person for any bacterial or fungal growth. Microscopy slides will be re-examined and a report prepared.

- Any bacterial growth will be identified by conventional methods (eg API and where appropriate, MALDI-ToF). Fungal growth will be identified to genus level. All isolated will be subcultured and stored as frozen.
- Bacterial isolates will be tested for susceptibility to the three drugs in the antimicrobial catheter. A disk test is available to rifampicin susceptibility. For sparfloxacin and triclosan susceptibility, agar-incorporation assays will be used.
- All data will be recorded and securely stored, with reference to the sample serial number allotted to them on receipt in the laboratory.

#### **Removed PD Catheters:**

#### Sample Collection

Removed PD catheters will be removed by the direct care team at University Hospitals of Derby and Burton NHS Foundation Trust. Any connectors, valves or accessories should be removed and discarded. The removed PD catheters will be packaged and labelled for transportation according to the World Health Organisation basic triple packaging system.

- The removed PD catheters and their attached cuffs should be placed in a specimen collection bag. This is its primary packaging.
  - If any of the cuffs were excised during removal, any detached cuffs should be placed in a sterile Universal container. There should be only 1 cuff per sterile Universal container. Therefore, if both cuffs were excised from the catheter, 2 sterile Universal containers will be required: one for each cuff

- The specimen collection bag should be labelled with the date the PD catheter was removed and the participant's study identifier.
- The specimen collection bag containing the PD catheter and any Universal containers should then be placed into a second sterile clear zip-lock bag containing an absorbent pad. This is the secondary packaging.
- The PD catheter and cuffs in their primary and secondary packaging should be then placed in an opaque, hard-side container for transportation. This is their transportation packaging. Transportation packaging should be labelled with 'UN3373 Biological Substance Category B' for transportation to the University of Nottingham.
- If the removed PD catheter and cuffs are not sent for transportation within one hour of removal, they should then be stored in their transportation packaging at 4-8oC.
- Once arriving at the laboratory, PD catheter and cuffs should be stored at 4-8IDC until it they are processed, which should be within 24 hours of collection.

## Sample Analysis

The PD catheters and their cuffs will be analysed for any microorganisms attached to the PD catheter or cuff material. Microorganisms will be isolated from the catheter and cuffs by sonication in a method similar to previously published methods for isolating microorganisms from urinary catheters (16,17)Any isolated microorganisms will then be identified and tested for antimicrobial resistance to the three antimicrobials of the PD catheter; rifampicin, sparfloxacin, and triclosan.

#### Storage

Microorganisms isolated from PD catheters and/or their cuffs may be stored for future reference and these will be stored at the University of Nottingham. Any microorganism isolates from PD catheters and/or their cuffs will not be linked to any patient identifiable information and will not contain any relevant material. Individual microorganism isolates will be stored in cryogenic vials at -20IIC.

#### Destruction

Removed PD catheters and their cuffs will not be retained for more than 2 weeks beyond the end of the study. Once analysis is complete they will be neutralised by incineration as part of clinical waste disposal. The laboratory records and CRF will be updated to demonstrate that the sample is no longer under the custodianship of the University of Nottingham.

It is the responsibility of the trial site to ensure that samples are appropriately labelled in accordance with the trial procedures to comply with the 2018 Data Protection Act. Biological samples collected from participants as part of this trial will be transported, stored, accessed and processed in accordance with national legislation relating to the use and storage of human tissue for research purposes and such activities shall at least meet the requirements as set out in the 2004 Human Tissue Act and the 2006 Human Tissue (Scotland) Act.

## 6.7. End of Trial

The end of trial will be defined as last patient, last visit. The Sponsor will notify the participating sites and REC within 90 days of the end of trial. The clinical trial report will be written within 12 months of the end of trial.

#### 7. INVESTIGATIONAL DEVICE

## 7.1. Name and Description of Investigational Device(s)

#### **Device description**

The device under investigation is the antimicrobial PD catheter (APDC) which is an all-silicone PD catheter that is impregnated with three antimicrobials: 0.922% w/w triclosan (CAS 3380-34-5), 0..509% w/w sparfloxacin (CAS 110871-86-8), and 0.057% w/w rifampicin (CAS 13292-46-1). The APDC consists of a base CE-marked all-silicone PD catheter that is then modified by the antimicrobial impregnation process described in the patent entitled 'Medical devices and methods of making medical devices' (Publication No WO2006/032904).

Catheter description	Catheter length	Catheter outer	Catheter inner
		diameter	diameter
Adult, Coiled Tenckhoff 2 cuff	575 mm	4.9 mm	2.6 mm
PD catheter			
Adult, Coiled Tenckhoff 2 cuff	630 mm	4.9 mm	2.6 mm
PD catheter			

The antimicrobial PD catheters will be manufactured in two sizes: Table 1

Table 1 Size and specification of PD catheters

The APDC is terminally sterilised by ethylene oxide and supplied as sterile to the direct care team. It should not be re-used or re-sterilised.

The materials used in the APDC and its manufacturing and their contact with the body can be found in Table 2below. According to ISO 10993-1 the APDC is an externally communicating medical device and the device is in contact with the patient's peritoneum and skin at the exit site.

Function / Process	Component	Materials	Body Contact		
Base silicone PD catheter	Shaft	Medical grade silicone rubber tubing	Yes		
		Radiopaque X-ray stripe	Yes		
	Cuffs (2)	Dacron (polyethylene terephthalate)	Yes		
		<need base="" catheter
supplier></need>	No		
Impregnation	Antimicrobials	Rifampicin (0.057% w/w)	Yes		
		Sparfloxacin (0.509% w/w)	Yes		
		Triclosan (0.922% w/w)	Yes		
Solvent	Impregnation	Chloroform (Reduced to nil)	Yes, if any		
	reagents		residues		
Rinsing		0.1N Sodium hydroxide (Reduced to	Yes, if any		
		nil)	residues		
Sterilisation	Residuals	Ethylene oxide	Yes, if any residues		

Table 2 Summary of Materials and Body contact

All three antimicrobials used in the manufacture of APDCs meet the pharmaceutical standards for manufacturing and have the accreditations and supporting documentation in Table 3to support their safe use.

Active ingredient	Name of manut	facturer	GMP certifyi	ng body	DMF	WC	COA	CTD access
Rifampicin	Name (commercially can provide is re	redacted sensitive, equested)	China Food Administratio	-	Yes	Yes	BP2019	Yes
Sparfloxacin	Name (commercially can provide is re	redacted sensitive, equested)	Drugs Administratic Telangana	Control on -	No	No	Inhouse	No
Triclosan	Name (commercially can provide is r	redacted sensitive, equested)	Central Drugs Standard Control Organisation- India, Food and Drug Administration -USA		No	Yes	USP	No

*Table 3* Supplier of antimicrobials for APDC manufacture with accompanying accreditation and documentation. GMP: Good Manufacturing Practice, DMF: Drug Master File, WC: Written Confirmation, COA: Certificate of Analysis, CTD: Common Technical Document, USP: United States Pharmacopoeia,

#### Intended purpose

The primary purpose of the APDC is for access to the peritoneal cavity through which dialysis fluid is administered for acute and chronic peritoneal dialysis therapies. The antimicrobials are present in the catheter secondarily to protect the catheter from bacterial attachment which could lead to infection.

Neither the APDC nor the antimicrobials contained in it are intended for therapeutic application to treat infection.

#### Intended user

Antimicrobial Peritoneal Dialysis Catheters should be implanted and/or explanted by a physician experienced with percutaneous and/or surgical placement and familiar with the complications of their use.

#### Intended populations

The antimicrobial PD catheter is intended for use in adults. Contraindications include:

Absolute

- Allergy to rifampicin, sparfloxacin or any other fluoroquinolone antibiotic, and / or triclosan
- Presence of stoma
- Presence of large inoperable hernia
- Known peritoneal fibrosis
- Severe obesity

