#### 5. ELIGIBILITY CRITERIA

All patients who opt for peritoneal dialysis (PD) will be invited to participate, subject to the following inclusion and exclusion criteria.

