## 5.1. Inclusion Criteria

Aged 18 years or older End stage kidney disease (ESKD) of any cause Elective PD catheter insertion

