#### 5.2. Exclusion Criteria

Documented allergy to rifampicin, sparfloxacin (or any fluoroquinolone), triclosan, or silicone Pregnant, likely to become pregnant, or breastfeeding Emergency PD catheter insertion

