#### 6.2. Consent

Informed consent must be obtained prior to the participant undergoing procedures that are specifically for the purposes of the trial (including the collection of identifiable participant data, unless the trial has prior approval from the Confidentiality Advisory Group (CAG) and the REC.

The Principal Investigator (PI) retains overall responsibility for the informed consent of participants at their site and must ensure that any person delegated responsibility to participate in the informed consent process is duly authorised, trained and competent according to the REC approved CIP, principles of Good Clinical Practice (GCP) and Declaration of Helsinki.

Once individuals have been identified as eligible for inclusion they will be provided with a patient information sheet (PIS) and given time to consider the information. If they indicate that they are willing to participate they will then have a meeting with a member of the study team who will take consent for the study after answering any questions that they may have. Participants will still need to be consented separately by the clinical team for the PD catheter insertion procedure.

Only individuals who have capacity to consent are eligible to be recruited to this study. If they lose capacity at a later point they will continue within the study unless they have withdrawn consent prior to losing capacity. Any potential participant has the right to refuse participation without giving reasons

and this will not alter their care in any way. If required a trained interpreter will be provided. The PI takes responsibility for ensuring that all vulnerable subjects are protected and participate voluntarily in an environment free from coercion or undue influence.

If a participant wishes to withdraw from the study then no further data (aside from safety data) will be collected with regards to that individual. The PD catheter will remain in situ until such time as it is decided by the clinical team that it should be removed for clinical reasons.

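### Four of the five absolute contraindications to the study catheter in Section 7.1 have no counterpart in the Section 5 eligibility criteria or the Trial Summary

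*Protocol*

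**What the plan says.** Section 5 opens with a broad invitation: "All patients who opt for peritoneal dialysis (PD) will be invited to participate, subject to the following inclusion and exclusion criteria". The inclusion criteria in Section 5.1 are, in full, "Aged 18 years or older End stage kidney disease (ESKD) of any cause Elective PD catheter insertion". The exclusion criteria in Section 5.2 are, in full, "Documented allergy to rifampicin, sparfloxacin (or any fluoroquinolone), triclosan, or silicone Pregnant, likely to become pregnant, or breastfeeding Emergency PD catheter insertion". The Trial Summary carries the same lists.

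Section 7.1, under Intended populations, has a different list: "The antimicrobial PD catheter is intended for use in adults. Contraindications include". It divides the items into absolute and relative. The first absolute item is "Allergy to rifampicin, sparfloxacin or any other fluoroquinolone antibiotic, and / or triclosan". The remaining absolute items are a stoma, "Presence of large inoperable hernia", known peritoneal fibrosis and severe obesity. No threshold is given for the last. Three relative items follow, concerning earlier major abdominal surgery, aortic aneurysm and repeated hernias.

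**The concern.** Both lists bear on who may receive the device, and both stand in the same plan, yet they give different answers. The device is a Class III investigational implant (Section 7.1, Medical device classification), and the primary objective is its safety and tolerability in a single arm of 40. For someone with one of the four unmatched conditions, staff working from Section 5 would find no bar to entry, while staff working from Section 7.1 would find an absolute one. The plan does not say which section settles the matter.

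The main stake is participant safety: by the plan's own account, these are people in whom this catheter should not be used. The second is consistency of the enrolled population. If two members of staff can reach different decisions on the same patient from the same document, the group whose adverse event rate is reported is not clearly defined.

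**Working it through.** No arithmetic decides this point, so the check sets the items side by side.

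**Step 1. Absolute contraindications (Section 7.1) against the Section 5 criteria and the Trial Summary.**

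| Absolute contraindication in 7.1 | In 5.1 | In 5.2 | In Trial Summary |
|---|---|---|---|
| Allergy to the antimicrobials | no | yes | yes |
| Stoma | no | no | no |
| Large hernia that cannot be operated on | no | no | no |
| Known peritoneal fibrosis | no | no | no |
| Severe obesity | no | no | no |

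Result: 1 of 5 matched, 4 of 5 unmatched. The three relative items are not in Section 5 either. A relative contraindication leaves room for clinical judgement, so that absence is not in itself a contradiction.

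**Step 2. Does another step bring the Section 7.1 list into screening?**

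- Section 6.1.1 (Patient Identification) and Section 6.1.2 (Screening) describe when and by whom patients are approached. Neither refers to Section 7.1 or names any of the four conditions. Section 6.1.2 includes people returning to PD who need a new catheter.
- Section 6.2 (Consent) adds one eligibility condition, "Only individuals who have capacity to consent are eligible to be recruited to this study", and none of the four.
- Section 6.3 (Baseline Data) lists the medical history to be collected without naming stoma, hernia or peritoneal fibrosis. Height and weight are recorded but not tied to eligibility.
- The schedule in Appendix 1 has no row for checking contraindications.

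Result: no step closes the gap.

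**Step 3. A test case.** Take an adult with end-stage kidney disease, due for elective insertion, with a stoma, no relevant allergy, and neither pregnant nor breastfeeding. All three inclusion criteria are met and none of the three exclusion criteria applies, so this person is eligible under Section 5. Section 7.1 calls the device absolutely contraindicated. The same holds for each of the other three conditions.

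**The case against.** The strongest reply is that ordinary clinical selection does this work. Participants come from patients already known to the renal team (Section 4). They are approached after the decision to have PD has been made, with extensive counselling (Sections 6.1.1 and 6.1.2). The clinical team takes separate consent for the insertion (Section 6.2), and Section 7.1 expects the implanting physician to be experienced and familiar with the complications. The investigator brochure, the instructions for use and the screening CRF are not at hand and may carry the contraindications. This stands as a reason to think few such patients would be enrolled. It does not make the lists agree, because the protocol does not say that any of these steps screens for the four conditions.

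A reader might also infer more than the documents support:

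- **That Section 5 must prevail because Section 12.4 forbids planned deviations and waivers.** Section 12.4 binds staff to the whole plan, which includes Section 7.1. It does not rank one section above the other. The capacity condition in Section 6.2 shows that an eligibility rule can sit outside Section 5.
- **That adverse events in such participants could not be told apart from effects of the impregnation.** That is too strong. The primary endpoint concerns events attributable to the antimicrobials or the impregnation process, and Section 8.3.1.2 requires a causality judgement for each event, in which another cause can be recorded.
- **That the adverse event rate would be distorted by some stated amount.** The documents give no prevalence for the four conditions and no event rate in people who have them.
- **That silicone allergy and capacity to consent are further gaps.** Silicone allergy is in Section 5.2 though not in Section 7.1, and Section 6.2 already makes capacity a condition of recruitment. Both groups are excluded as the plan stands, so these are drafting matters.

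**Conclusion.** The contradiction is real and should be corrected. Four of the five absolute contraindications in Section 7.1 are missing from Section 5 and the Trial Summary, and no screening, consent or baseline step supplies them.

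The finding concerns what the written criteria permit. It is not evidence that contraindicated patients will be enrolled, and their number cannot be estimated from the protocol. It assumes that the lists in Sections 5.1 and 5.2 are complete, as Section 5 presents them, and that the unseen screening CRF does not already apply the Section 7.1 list. If the CRF does, the practical risk is smaller, but the protocol text still needs to agree with itself. Which list is clinically right is not judged here.

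**What to change.** Reconcile Section 5, Section 7.1 and the Trial Summary so that one list governs screening. The clinical team should decide its content, including how severe obesity is to be defined if it stays on the list and how the relative items are to be handled. Section 6.1.2 should point to that list, and the screening CRF should carry each item so that the check is documented.

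The direct cost is an amendment of the eligibility text and a CRF change. The possible downside is a few fewer eligible patients. Section 10.2 expects 50 × 1.5 = 75 catheters in 18 months and so needs 40/75 = 53% of those patients to join. The documents do not say how many would become ineligible if exclusions were added. As assumptions only, losses of 5%, 10% and 20% would give:

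- 5%: 40/(75 × 0.95) = 40/71.25 = 56%
- 10%: 40/(75 × 0.90) = 40/67.5 = 59%
- 20%: 40/(75 × 0.80) = 40/60 = 67%

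The 75 is based on catheters the unit has placed in practice. If routine selection already keeps these patients from having a catheter, the loss would be close to nil.

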#### Relative

- Previous major abdominal surgery
- Abdominal aortic aneurysm
- Multiple previous abdominal hernias

#### Packaging and labelling

All APDCs will be individually packaged in a primary packaging sterile barrier and packing will be carried out in a Class ISO 14644 Class 8 Cleanroom.

Each catheter will be individually labelled with a Primary Product Label in accordance with ISO 15223-1: 2016. The Primary Product Label will include a catheter sizing diagram, harmonised symbols and information that the catheter is 'exclusively for clinical evaluation'.

# Description of the specifical medical or surgical procedures involved in the use of the investigational device.

The use and insertion of the antimicrobial PD catheter is no different from the use and insertion of a standard PD catheter.

PD catheters are manufactured from silicone tubing. One end has several perforations in the silicone to assist drainage and this end is also curled ("pig-tailed") to assist placement in the pelvis. The other end is left "plain" and is designed to receive a sterile plastic connector with a screw thread for connection to a further silicone tube that has an opening/closing device which in turn connects to a bag of PD fluid. When not in use, a sterile cap is applied to the end of the catheter to prevent contamination. PD catheters are produced in different lengths to suit the body size of different patients.

PD catheters are placed, either percutaneously (with local anaesthetic) employing a Seldinger technique (guidewire) assisted by real-time x-ray imaging to facilitate correct positioning or surgically via laparoscopy requiring general anaesthetic. The perforated (proximal) end of the catheter is placed in the pelvis. The distal end is externalised below the umbilicus and then tunnelled laterally through the subcutaneous fat to an exit site 10-15 cm lateral to the midline on the left or right, depending on patient preference and or anatomical considerations.

The subcutaneous portion of the catheter has two Dacron cuffs attached to secure the catheter in the subcutanous tissues After several weeks, fibrosis around the Dacron cuffs fixes the catheter in the subcutaneous tissue. A surgical dressing is applied to the exit site and changed regularly to protect in from infection. Patients are thoroughly trained in the use of aseptic technique to be applied when PD fluid exchanges are performed.

#### **Risk assessment summary**

The risks associated with the APDC are either well-understood in that they are risks of all PD catheters or are unique to antimicrobial impregnation process. Firstly, those risks associated with all PD catheters are accepted risks that are well-characterised and understood as PD catheters are currently in use world-wide. The base CE-marked catheter (which is subsequently modified by antimicrobial impregnation) has achieved the CE-mark because the risks associated its manufacture and with PD catheterisation are understood and are mitigated as far as possible.

Secondly, the process of antimicrobial impregnation does introduce additional risks that are relatively unique. However, these risks are controlled for using in-process controls and finished product testing before the AMUCs are available for clinical use. The risks associated with antimicrobial impregnation can be mitigated with the current processes and controls in place. The risks are likely to be outweighed by the potential prevention of peritonitis and exit site infections, which are significant adverse events that can potentially lead to serious consequences such as hospitalisation, sepsis, and potentially death.

